8.0 DRUG INFORMATION

8.1 Description

EXE is an oral, irreversible, steroidal aromatase inactivator, structurally similar to the natural substrate, androstenedione. In postmenopausal women, estrogens are produced primarily by the conversions of androgens into estrogens through the aromatase enzyme in peripheral tissues. By acting as a false substrate and irreversibly binding to the active site of the aromatase enzyme, EXE causes inactivation of the aromatase enzyme,

resulting in significant inhibition of circulating estrogen concentrations in postmenopausal women, but has no detectable effect on adrenal biosynthesis of corticosteroids or aldosterone. In postmenopausal breast cancer patients treated with 25 mg of EXE daily, whole body aromatization was suppressed by greater than 90%. EXE is currently approved by the FDA for use in the treatment of postmenopausal women with advanced breast cancer, whose disease has progressed following tamoxifen therapy. EXE is also approved for use as adjuvant therapy for postmenopausal women with estrogen receptor positive breast cancer. The recommended dose of EXE is 25 mg orally once daily after a meal.

8.2 Toxicology

In clinical trials of 1058 postmenopausal women with advanced breast cancer, daily doses of EXE consisting of 25 mg, was generally well tolerated and adverse events were usually mild to moderate. Adverse effects of EXE which have been reported among postmenopausal women receiving this therapy in either the adjuvant or metastatic setting, include:

More Common

Endocrine/metabolic: diaphoresis (6-17.8%), hot sweats (13-32.9%) Gastrointestinal: nausea (8.5-18%), diarrhea (4-9.6%), vomiting (7%)

Musculoskeletal: arthralgia (14.6-28.8%), myalgia (5.5%), osteoporosis (4.6%), pain in limb (9%), osteoarthritis (5.9%) Neurologic: headache (6.9-13.1%), insomnia (11-13.7%), dizziness (8-9.7%) Constitutional: fatigue (11-22%), asthenia (6%) Dermatologic: alopecia (15.1%), dermatitis (8.2%) Psychiatric: depression (6.2-13%), anxiety (4.1-11%)

Severe

Cardiovascular: heart failure (0.4%), myocardial infarction (1.6%) Musculoskeletal: fracture of bone (4.2%) Neurologic: cerebrovascular accident (6 deaths due to stroke, N=2252) Hematologic: thromboembolic event (0.9%)

8.3 Pharmacology

Kinetics: EXE is rapidly absorbed after oral administration and high-fat food increases plasma levels. It is metabolized hepatically via the CYP3A4 pathway and converted into an active 17-dihydro metabolite. Routes of systemic excretion of EXE consist of fecal (42%) and renal (42%), with < 1% of drug remaining unchanged. Elimination half life is 24 hours. Based on experience with EXE in multiple doses up to 200 mg daily, the manufacturer does not recommend dosage adjustment in patients with renal or hepatic impairment. In postmenopausal women, suppression of plasma estrogen was observed 8-24 h after single oral doses of EXE [20].

Formulation: EXE is supplied as a 25 mg tablet.

Storage and Stability: Store at controlled room temperature, 25[°] C.

Administration: Oral

Supplier: This study will supply all study participants with EXE, as provided by the manufacturer (Pfizer).

9.0 REGULATORY OBLIGATIONS

9.1 Informed Consent

All patients will have signed an informed consent for participation in research activities, according to all institutional, NCI and federal regulations and will have been given a copy of the Experimental Subject's Bill of Rights. The original signed consent form will be placed in the medical record. A copy will be given to the subject and a copy will be filed in the research record.

9.2 Confidentiality of Records

The study protocol will strictly adhere to all HIPAA and COH IRB regulations. Confidentiality of subjects will be strictly maintained. All research records and data collection forms will be stored in secured cabinets at the data coordinating center at COH.

9.3 Registration Process

- 9.3.1 Registrations for this protocol must be made through the CRIM office at the City of Hope between the hours of 8:30 a.m. to 4:30 p.m., Monday through Friday (except holidays).
- 9.3.2 Patients must be registered within 2 weeks prior to initiation of protocol therapy.
- 9.3.3 A patient failing to meet all protocol requirements may not be registered. If you have any questions regarding eligibility, contact [contact] [name] and ask for the CRA in charge of this study.
- 9.3.4 Pre-study laboratory tests, scans and x-rays must be completed prior to registration according to study calendar.
- 9.3.5 Patients must sign an informed consent prior to registration.
- 9.3.6 Confirm that the patient meets all inclusion and exclusion eligibility criteria for this protocol.

- 9.3.7 Complete the eligibility checklist.
- 9.3.8 Verify that all required pre-study tests were performed.
- 9.3.9 Fax the completed eligibility checklist and the signed, dated informed consent to CRIM. The FAX number is [contact].
- 9.3.10 Call the CRA at [contact] [name] to confirm the FAX arrival. If the coordinator is not in the office, have her paged.
- 9.3.11 If the patient qualifies, the City of Hope coordinator will assign the patient's study ID number.
- 9.3.12 Once a patient has been registered, the CRA will confirm registration of the patient.

9.4 Data Collection Forms and Submission Schedule

All data will be collected using COH Biostatistics Information Tracking System (BITS) data collection forms. Forms to be completed include:

Eligibility Checklist:	This form will be completed at the time of registration.
On-Study Form:	To be completed within two weeks of registration.
Treatment Form:	To be completed within four weeks of completion of one cycle of treatment.
Flow Sheets:	Protocol specific flow sheets are to be submitted along with each treatment form.
Response/Off-Study/	
Follow-Up:	Form F/U is to be submitted each time a patient is evaluated for response and/or new follow-up information is obtained.
Supplemental	
Data Form :	The timeline for submission of the supplemental data form will be protocol specific, if applicable.

Additionally, Health Assessment Questionnaires (Appendix A), EORTC Quality of Life Questionnaires (Appendix C) and treatment diaries will be collected per study calendar (section 10).

10. STUDY CALENDAR

STUDY CALENDAR

	Screen									St	udy 1	Treat	nent								Study Termination
Cycle			1			2			3			4			5			6			
Cycle Days⁵		1	8	15	1	8	15	1	8	15	1	8	15	1	8	15	1	8	15		
Study Week		1	2	3	4	5	6	7	8	9	10	11	12	13	14	15	16	17	18	Consent	
Treatment Schedule ⁵																				Suc	
Exemestane		Х	Χ	OFF	Χ	Χ	OFF	X	Χ	OFF	Χ	Χ	OFF	Х	X	OFF	X	X	OFF	ŭ	
GENERAL ASSESSMENTS																				Toxicity, ath	
Informed consent	Х																			о Хіс	
Review of Eligibility	Х																				
Medical History/Clincal Evaluation ¹	Х							Х									Х			Unacceptable scretion or Dea	
Weight/Height/Vitals	Х							Х									Х			PD, Unacceptab PI Discretion or I	
Prior & Current Medication List	Х	х			X			Х			x			х			x			acc etic	
Assessment of Compliance/Toxicity								Х									X			Un scr	
LABORATORY ASSESSMENTS																				PI Di	
Blood Chemistry ⁶	Х	х			х			Х			х			х			Х			= -	
Hematology ⁶	Х	Х			Χ			Х			Х			Х			Х			ur wal	
																				Assessments Uni Withdrawal,	
																				/ith	
TUMOR RELATED ASSESSMENTS																				<pre>Ses</pre>	
Bone Scan ²	Х									х									X	Ass	
Radiologic Assessments ³	Х									Х									Х		
																				Continue	
Quality of Life (Appendix C)		Х			Х			Х			Х			Х			Х			Cor	X
Tumor Sample ⁴	Х																				x
HAQ Questionnaire (Appendix A)		x			x			x			х			x			x				

 ¹Clinical evaluation including physical examination and assessment of performance status (ECOG Score)

 ²Patients with a positive bone scan at screening *[note: PET/CT Scan may be used in lieu of Bone Scan when patient is symptomatic]* will continue to have bone scans performed every 9 weeks while on study. Subjects with a negative bone scan at the start of study will not be required to continue with follow-up bone scans, unless clinically indicated.

 ³Radiologic assessments may be performed by CT or MRI but the same modality used at the time of screening must be used throughout the study. Studies will be repeated every 9 weeks.

 ⁴Tumor samples of primary and metastatic sites (archived block, slides or fresh tissue collected for clinical care purposes), will be collected at study initiation. If possible, pre- and post-treatment biopsy specimens will also be obtained.

 ⁵ All tests, procedures and treatment will have +/- 3 day window.

 ⁶ Research Patient Numbers (RPNs) will be used as identifiers for blood samples collected. After Cycle 6, Blood Chemistry and Hematology will be done per MD discretion.

REFERENCES

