- To be assigned a status of PR or CR, changes in tumor measurements must be confirmed by repeat assessments that should be performed no less than 4 weeks after the criteria for response are first met. Longer intervals as determined by the study protocol may also be appropriate.
- In the case of SD, follow-up measurements must have met the SD criteria at least once after study entry at a minimum interval (in general, not less than 6-8 weeks) that is defined in the study protocol

Duration of overall response

• The duration of overall response is measured from the time measurement criteria are met for CR or PR (whichever status is recorded first) until the first date that recurrence or PD is objectively documented, taking as reference for PD the smallest measurements recorded since the treatment started.

Duration of stable disease

• SD is measured from the start of the treatment until the criteria for disease progression are met, taking as reference the smallest measurements recorded since the treatment started.

5.3 Toxicity Assessments

To protect against and minimize potential risks, assessments of treatment-related toxicities will be performed by the study nurse every three weeks (via telephone). The NCI, Common Toxicity Criteria for Adverse Events (CTCAE, version 3.0, available at http://ctep.cancer.gov//forms/CTAEv3.pdf)), will be used as a guide to assess severity. To assess musculoskeletal adverse effects associated with EXE use, all subjects will complete modified Health Assessment Questionnaires (HAQ DI©) (Appendix A) at the start of each cycle of treatment, as previously validated [7, 17].

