7.4 Reporting of Unanticipated Problems and Adverse Events

Unanticipated Problems: Most unanticipated problems must be reported to the COH DSMC and IRB **within 5 calendar days** according to definitions and guidelines at http://www.coh.org/hrpp/Pages/hrpp-policies.aspx. Any unanticipated problem that occurs during the study conduct will be reported to the DSMC and IRB by submitting electronically in iRIS (http://iris.coh.org).

Serious Adverse Events - All SAEs occurring during this study, whether observed by the physician, nurse, or reported by the patient, will be reported according to definitions and guidelines at http://www.coh.org/hrpp/Pages/hrpp-policies.aspx and Table 2 below. Those SAEs that require expedited reporting will be submitted electronically in iRIS (http://iris.coh.org/).

Adverse Events - Adverse events will be monitored by the PMT. Adverse events that do not meet the criteria of serious OR are not unanticipated problems will be reported only in the protocol continuation reports and PMT report (see Table 2 below).

Table 2: City of Hope Adverse Event and Unanticipated Problem Reporting Timelines for the DSMC and IRB

Required Reporting Timeframe to DSMC		
Attribution	UNEXPECTED	EXPECTED

Required Reporting Timelines to DSMC for AE/SAEs Investigator Initiated Studies

	Death while on active treatment or within 30 days of last day of treatment	
Possibly, Probably, Definitely Unlikely, Unrelated	5 calendar days	
	Death after 30 days of last	t active treatment/therapy
Possibly, Probably, Definitely	5 calendar days	No reporting required
Unlikely, Unrelated	No reporting required	No reporting required
	Grades 3 and 4 AND meeting the definition of "serious"	
Possibly, Probably, Definitely	5 calendar days	10 calendar days
Unlikely, Unrelated	5 calendar days	10 calendar days
	Grades 1 and 2 AND resulting in "hospitalization"	
Possibly, Probably, Definitely	5 calendar days	10 calendar days
Unlikely, Unrelated	10 calendar days	10 calendar days

Externally Sponsored Studies

Required Reporting Timeframe to DSMC		
Attribution	UNEXPECTED ¹	EXPECTED
	Death while on active treatment or within 30 days of last day of treatment	
Possibly, Probably, Definitely	No DSMC reporting required - IRB reporting may be necessary	
Unlikely, Unrelated		
	Death after 30 days of las	t active treatment/therapy
Possibly, Probably, Definitely	No DSMC reporting required - IRB reporting may be necessary	
Unlikely, Unrelated		

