	Grades 3 and 4 AND meeting the definition of "serious"	
Possibly, Probably, Definitely	No DSMC reporting required - IRB reporting may be necessary	
Unlikely, Unrelated		
	Grades 1 and 2	
Possibly, Probably, Definitely	No DSMC reporting required - IRB reporting may be necessary	

An event determined by the IRB of record to be an Unanticipated Problem (UP) will be communicated to the Investigator and COH DSMC through the COH IRB Operations Director. The DSMC will review the case and make a determination as to whether the study will be suspended, terminated, amended, or allowed to continue without amendment.

Required Reporting Timeframe to IRB of Record								
Attribution	UNEXPECTED	EXPECTED						
	De	ath						
Possibly, Probably, Definitely	5 calendar days	Annual						
Unlikely, Unrelated	Annual	Annual						
	Grades 3 and 4 AND meeting the definition of a UP							
Possibly, Probably, Definitely	5 calendar days	Annual						
Unlikely, Unrelated	Annual	Annual						
	Grade 1 and 2 AND meeting the definition of a UP							
Possibly, Probably, Definitely	5 calendar days	Annual						
Unlikely, Unrelated	Annual	Annual						

Additional Reporting Criteria

Pfizer

In addition to requirements of reporting of adverse events to the COH DSMB and IRB, serious adverse events resulting in death or considered life threatening will be submitted to Pfizer within 24 hours of awareness, via FDA MedWatch Form 3500A-Mandatory Reporting, obtained from the FDA website (http://www.fda.gov/medwatch/report/hcp.htm). The period that serious adverse events will be reported to Pfizer will be from the occurrence after the first dose of EXE, through 28 days after discontinuation of study treatment.

Fax FDA MedWatch Form 3500A to:

Pfizer U.S. Clinical Safety [contact]

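### The study calendar schedules the QLQ-C30 but neither the HAQ nor a toxicity check at Study Termination, so the HAQ series can understate joint toxicity in patients who stop mid-cycle

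*Combined protocol and SAP*

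**What the plan says.** Section 1.2 makes toxicity a secondary objective, and section 5.3 chooses the HAQ to measure musculoskeletal effects. The form is due "at the start of each cycle of treatment, as previously validated". Section 9.4 says that HAQ forms, QLQ-C30 forms and diaries "will be collected per study calendar (section 10".

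In the calendar, the row "HAQ Questionnaire (Appendix A" is marked on Day 1 of cycles 1 to 6 and is empty under Study Termination. The row "Assessment of Compliance/Toxicity" is marked only at weeks 7 and 16 and is also empty there. The row "Quality of Life (Appendix C" has the same cycle marks as the HAQ plus a mark under Study Termination. The only other row marked in that column is the tumor sample.

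On toxicity more broadly, section 5.3 has the study nurse telephone every three weeks and gives no end date. Section 7.3 counts events after treatment as adverse events. Section 7.4 sets the period for SAE reports to the manufacturer as "from the occurrence after the first dose of EXE, through 28 days after discontinuation of study treatment", and its DSMC table has a category for "Death while on active treatment or within 30 days of last day of treatment". Section 3.5 gives one year of follow-up without stating its content.

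**The concern.** A HAQ value is lost when a patient stops, and one reason for stopping is the toxicity that the HAQ is meant to measure. The loss is therefore related to the outcome. Patients whose joint symptoms worsen enough to end treatment leave the series on their last, better score.

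This matters more here than in a randomized trial because no concurrent arm shares the loss. Section 6.1 also treats PFS equivalent to historical data as success, on the assumption that less drug means less toxicity. The toxicity data are the only check on that assumption, and a gap that makes them look milder favours the regimen.

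A second, smaller issue is that the plan sets reporting windows of 28 and 30 days after treatment but schedules no contact at which events in those windows would be asked about.

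**Working it through.** **1. A mid-cycle stop, followed through the schedule.** Inputs: 21-day cycles with drug on Days 1-14 and none on Days 15-21 (section 3.2); HAQ on Day 1 of each cycle (section 5.3 and calendar); HAQ recall of one week (Appendix A).

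- Cycle 2 starts on study Day 22. A patient who develops joint symptoms and stops on Day 30 is on cycle Day 30 - 21 = 9.
- Her last HAQ is from Day 22. Its recall week is Days 15-21, which is exactly the off-drug week. The calendar's 3-day window can shift this by a few days.
- The next HAQ would be due on Day 22 + 21 = 43. She does not start that cycle, and the termination cell is empty, so no further form is due.
- A patient who stops during cycle 1 has only the Day 1 form, completed at the start of treatment.

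**2. The toxicity row for the same patient.** Week 7 starts on Day 6 x 7 + 1 = 43, and week 16 on Day 15 x 7 + 1 = 106. The calendar therefore gives her no toxicity assessment before she stops. Section 5.3 gives her calls every three weeks, which the calendar does not show. The two places disagree and must be reconciled.

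**3. Contact after the last dose.** The 28-day and 30-day items in section 7.4 say what must be reported and how fast. No visit or call is dated to fall at the end of either window. Section 5.3 does not say whether the calls continue after the last dose, and section 3.5 does not say what follow-up contains.

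**4. Size of the HAQ bias.** Understatement of mean worsening = (share who stop with an unrecorded worsening) x (size of that worsening). The documents give neither factor, so no figure follows.

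**5. The one stated design figure that depends on toxicity ascertainment.** Section 6.1 states 81% power for joint disorders: 30% versus 15%, n = 36, one-sided exact test at nominal 10%.

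- Exact binomial, declaring a reduction at 6 or fewer events: size 5.4%, power 71.0%.
- At 7 or fewer: size 11.2%, power 83.8%.
- Normal approximation without continuity correction: power 80.9%, which matches the stated 81%.

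That mismatch is a separate matter. To show direction only, suppose a share m of joint events went unrecorded and the true rate were 30%. The recorded rate is 0.30 x (1 - m), and the chance of wrongly declaring a reduction is P(X <= 6 | n = 36):

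- m = 0: 5.4%
- m = 10%: 11.0%
- m = 20%: 20.5%
- m = 30%: 34.5%

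Here m is an assumption, not an estimate of what the empty cells would cost. The plan does not define joint disorders by HAQ score, and an event that ends treatment would normally be known from the reason for stopping.

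**The case against.** The best reply is that toxicity capture does not depend on the termination column. The nurse calls have no stated end, post-treatment adverse events are within the definition, SAEs and deaths have reporting duties, follow-up runs for a year, and an off-study form exists. The QLQ-C30 at termination also asks about pain (items 9 and 19) and physical function (items 1-5). No stated test uses the mean HAQ. All of this stands, and it limits the point to the HAQ series, a systematic toxicity grade at stopping, and the later course of non-serious events such as arthralgia. It does not supply the missing HAQ, and it does not say when the calls end.

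Some stronger readings are tempting but not supported:

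- **That SAEs or deaths in the window are missed.** The documents show an unscheduled contact, not missed events. Deaths also count in PFS.
- **That joint toxicity is the expected route off study.** Section 2.0 links musculoskeletal effects to non-compliance but gives no stopping rate, and it expects every patient to progress eventually.
- **That the HAQ bias is 0.05 to 0.20 points.** This needs 10-20% stopping for joint symptoms with an unrecorded worsening of 0.5-1.0 (0.10 x 0.5 to 0.20 x 1.0). Neither range has a source in the documents. Against the arthralgia rates in section 8.2 (14.6-28.8%), 10% stopping would be 35-68% of all patients with arthralgia, and 20% would be 69-137%.
- **That the 30-day window, as a share of reportable time, measures the loss.** The formula 30/(T + 30) gives 33% at T = 61 days (2 months), 23% at 103 days (14.7 weeks), 21% at 113 days (3.7 months) and 9% at 304 days (10 months). These are shares of elapsed time, not of events missed.

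**Conclusion.** The point holds as a scheduling gap with a known direction and an unknown size. As written, no HAQ is due when a patient stops, and from cycle 2 on the last one recalls the off-drug week. The HAQ series can therefore understate musculoskeletal toxicity in patients who stop for it. For toxicity in general, the plan is incomplete rather than silent: the calendar and section 5.3 disagree, and no contact is scheduled to match the 28-day SAE window.

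The conclusion rests on section 9.4 meaning what it says, namely that an empty calendar cell means no form is collected. It changes no sample size, error rate or primary-endpoint rule. It is a cheap improvement.

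**What to change.** 1. In the calendar, mark the HAQ and Compliance/Toxicity rows under Study Termination, where the QLQ-C30 is already completed.
2. State in section 5.3 that the nurse toxicity calls continue through one call at about 28-30 days after the last dose. That call should cover new events and the status of events ongoing at stopping.
3. Reconcile the calendar's toxicity row (weeks 7 and 16) with the three-weekly calls in section 5.3.
4. Report the termination HAQ with the date of last dose and the reason for stopping, and show stops for progression separately from stops for toxicity. Do not treat every termination form as an on-treatment value. Progression can itself worsen function, and scans fall in the off-drug week (Days 15-21 of every third cycle), so forms completed around a scan may recall little or no time on drug.

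Cost: a calendar and text amendment, plus one more questionnaire and one call per patient, for at most 36 patients.

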APPENDIX A: HEALTH ASSESSMENT QUESTIONNAIRE (HAQ DI©)

Name:

Date					
					_

Please place and "x" in the box which best describes your abilities OVER THE PAST WEEK:

ARE YOU ABLE TO:	WITHOUT ANY DIFFICULTY	WITH SOME DIFFICULTY	WITH MUCH DIFFICULTY	UNABLE TO DO					
DRESSING AND GROOMING									
Dress yourself, including shoelaces and buttons?									
Shampoo your hair?									
ARISING									
Stand up from a straight chair?									
Get in and out of bed?									
EATING									
Cut your own meat?									
Lift a full cup or glass to your mouth?									
Open a new milk carton?									
WALKING									
Walk outdoors on flat ground?									
Climb up five steps?									
Please check any AIDS OR DEVICES	Please check any AIDS OR DEVICES that you usually use for any of the above activities:								
Devices used for Dressing	Built up or sp	pecial utensils	Cru	ıtches					

Devices used for Dressing (button hook, zipper pull, etc.)	Built up or sp	ecial	utensils	Crutches
Special or built up chair	Cane	,	Walker	Wheelchair

Please check any categories for which you usually need HELP FROM ANOTHER PERSON:

Arising

	Dressing
--	----------

g and grooming

[figure not shown]
	Eating
--	--------

Walking

Please place an "x" in the box which best describes your abilities OVER THE PAST WEEK:

[figure not shown]
	WITHOUT ANY DIFFICULTY	WITH SOME DIFFICULTY	WITH MUCH DIFFICULT	UNABLE TO DO
ARE YOU ABLE TO:	DIFFICULT	DIFFICULT	DIFFICULT	10 00
HYGIENE		_		
Wash and dry your body?				
Take a tub bath?				
Get on and off the toilet?				
REACH				
Reach and get down a 5 pound object (such as a bag of sugar) from above your head?				
Bend down to pick up clothing from the floor?				
GRIP	_			
Open car doors?				
Open previously opened jars?				
Turn faucets on and off?				
ACTIVITIES				
Run errands and shop?				
Get in and out of a car?				
Do chores such as vacuuming or yard work?				

ENGLISH

Your PAIN: How much pain have you had IN THE PAST WEEK?

On a scale of 0 to 100 (where zero represents "no pain" and 100 represents "severe pain"), please record the number below.

Your HEALTH: Please rate how well you are doing on a scale of 0 to 100 (zero represents "very well" and 100 represents "very poor" health), please record the number below.

-1

